2.1.5 Pharmacokinetic variables

Concentrations of total alirocumab, total and free PCSK9 in serum are assessed before IMP (pre-dose) at baseline (Week 0), Week 4, Week 8, Week 10 (for Cohort 4), Week 12 (for Cohort 4) and end of the follow-up period of OLDFI period (Week 16 for Cohorts 1& 2 or Week 14 for Cohort 3).

Pharmacokinetic variable is the total alirocumab concentration at each time point. Depending on the timing of the sample versus the previous injection, Ctrough, Cmax and CFollow-Up will be defined as follows (see also [Table 3](#)):

- Cmax for Q2W and Q4W regimens: alirocumab concentration sample taken 5 days \pm 2 days after previous injection of alirocumab;
- Ctrough for Q2W regimen: alirocumab concentration sample taken between 8 and 21 days after previous injection of alirocumab (may be just prior the next injection);
- Ctrough for Q4W regimen: alirocumab concentration sample taken between 22 and 35 days after previous injection of alirocumab (may be just prior the next injection);
- CFollow-up for Q2W regimen: alirocumab concentration sample taken more than 21 days after last injection of alirocumab and no more than 14 weeks after last injection of alirocumab.
- CFollow-up for Q4W regimen: alirocumab concentration sample taken more than 35 days after last injection of alirocumab and no more than 14 weeks after last injection of alirocumab.

Alirocumab concentration and total and free PCSK9 concentration will be described by time-point following time windows as defined in [Table 3](#) and [Table 5](#).

2.1.6 Pharmacogenetic endpoints

Not Applicable.

2.1.7 Quality-of-life endpoints

Not Applicable.

2.1.8 Health economic endpoints

Not Applicable.

2.2 DISPOSITION OF PATIENTS

This section describes patient disposition for both patient study status and the patient analysis populations, for OLDFI period and for OLDFI/OLE combined period.

Screened patients are defined as any patient who met the inclusion criteria and signed the informed consent.

Included patients consist of all screened patients enrolled in the OLDFI period (patients not screened failed).

For patient study status in the OLDFI period, the total number of patients in each of the following categories will be presented in the clinical study report:

- Screened patients
- Screen failure patients and reasons for screen failure
- Included patients
 - Included but not treated patients and reason for not being treated;
 - Included and treated patients
- Patients who completed the OLDFI treatment period as per protocol
- Patients who did not complete the OLDFI treatment period as per protocol
- Patients who discontinued the OLDFI treatment by main reason for permanent treatment discontinuation
- Status at last study contact for patients not entering in the OLE period
- Patients participating in the OLE period

For all categories of patients (except for the screened categories) percentages will be calculated using the number of included patients as denominator.

In addition, patient study status in the OLE period will be provided: the total number of patients in each of the following categories will be presented:

- Patients treated during the OLE period (all patients who received at least one OLE IMP injection during the OLE period)
- Patients who completed the OLE treatment period as per protocol
- Patients who did not complete the OLE treatment period as per protocol
- Patients who discontinued OLE treatment by main reason for permanent treatment discontinuation

Patient with insufficient post-treatment follow-up will be described for each analysis study treatment period.

A patient is considered with insufficient post-treatment follow-up or without post-treatment follow-up in the following cases:

- If the patient is not assessed at the post-treatment follow-up phone call (for OLE period)/ final follow-up visit (for OLDFI period), or any on-site post-treatment visit

- If the patient has no follow-up phone call (for OLE period) or on-site post-treatment visit more than 9 weeks after the last IMP injection of the corresponding period.

All major deviations potentially impacting efficacy analyses, inclusion and drug-dispensing irregularities, and other important deviations will be summarized in tables giving numbers and percentages of deviations. These deviations are listed in the centralized monitoring plan.

Additionally, the following populations will be summarized:

- Included population.
- Efficacy population: mITT population
- Safety population
- Pharmacokinetics population
- Anti-alirocumab antibody population

Definitions of the study populations are provided in [Section 2.3](#).

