- Cohorts 1 and 2 (Q2W): Alirocumab injections will be prepared from vials by the pharmacist (or equivalent). Detailed instructions on preparation of injections from vials will be provided in a separate document. Alirocumab injections will be administered at Weeks 0, 2, 4, and 6. The Weeks 0 and 4 alirocumab injections will be administered at the clinical site by the site staff. The Weeks 2 and 6 alirocumab injections will be administered at the clinical site by the site staff or at the patient's home by a health care professional, depending upon local arrangements and preferences of the investigator/patient.
- Cohort 3 (Q4W): Alirocumab injections will be prepared from vials by the pharmacist (or equivalent). Detailed instructions on preparation of injections from vials will be provided in a separate document. Alirocumab injections will be administered at Weeks 0 and 4 at the clinical site by the site staff.
- Cohort 4 (Q4W): Alirocumab injections will be administered with prefilled syringes. Alirocumab injections will be administered Week 0, Week 4, and Week 8 at the clinical site by site staff.
- The lipid results from specimens obtained during the open-label dose finding treatment period will be masked for the clinical site/Investigator and patients. No attempts should be made by the investigator or patient to routinely have the patient's lipid values independently evaluated after entry into the open-label dose finding treatment period and until the final follow-up visit for Cohort 1, Cohort 2, and Cohort 3, and entry into the OLE period for Cohort 4. The sponsor and the DMC will closely monitor the lipid results during the 8-week open-label dose finding treatment period. If any safety concerns are noted during this period, including very low LDL-C levels (ie, LDL-C <50 mg/dL [1.30 mmol/L] on one or more occasion), then appropriate action will be taken by the Sponsor in consultation with the DMC.

Follow-Up Period, only for Cohorts 1 to 3:

- A follow-up period (off treatment) of 6 (Cohort 3) or 8 weeks (Cohorts 1 and 2) after the end of open-label dose finding treatment period visit. For these 3 cohorts, the final follow-up visit corresponds to 10 weeks after the last alirocumab injection administered during the open-label dose finding treatment period, since the last injection for Cohorts 1 & 2 is Week 6 and for Cohort 3 it is Week 4.

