8.1.2 Timing of administration

During the main dose finding treatment period the first alirocumab injection for each cohort will start at Week 0 (after each respective screening period and DMC agreement for Cohorts 2 and 3) as soon as possible after the call for inclusion using the treatment kit number provided by the IRT according to cohort number and body weight. The first injection after call for inclusion will be done at the site by the investigator staff. Patients will be monitored at the investigational site for at least 30 minutes after this first injection.

The investigator staff will administer subsequent injections on site at the clinic, according to the dosing schedule at approximately the same time of the day. On days where the clinic study visit coincides with dosing, the dose of study drug will be administered after all study assessments have been performed and all laboratory samples (including PK) collected. For visits where home injection is allowed, the health care professional will administer the injection at the patient's home, as described in the relevant manuals.

During the main dose finding treatment period, alirocumab will be administered subcutaneously every 2 weeks or every 4 weeks at approximately the same time of the day; however it is acceptable to have a window period of ± 3 days.

Follow-up period during the main phase without treatment

No alirocumab administration between W8 and W16 for Cohort 1.

No alirocumab administration between W8 and W16 for Cohort 2.

No alirocumab administration between W8 and W14 for Cohort 3.

There is no follow up period for Cohort 4.

During the open-label extension period for Cohorts 1 & 2 the first injection administration will start at Week 16 after the last injection administration at Week 6 (ie, 10 weeks after the last administration of alirocumab. The treatment kit(s) number(s) will be provided by IRT according to the last dose administered in Cohort1/Cohort 2. The first injection of the extension period will be done at the site by the investigator staff. If the self-injections by patient or another designated person (such as parent, nurse, etc.) are decided during the extension period a training injection should be planned 2 weeks before the first self-injection, under direct site staff supervision.

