10.1.3 Follow-Up Period

The follow-up period is mandatory for cohorts 1-3 but not for Cohort 4.

10.1.3.1 First Follow-Up Visit (Visit 7 / Week 10/Day 70 ±7 [Cohort 3] / Week 12/Day 84 ±7 [Cohorts 1 & 2]) at clinical site or phone call if no safety concerns by the investigator at the previous visit or between the 2 visits “visit 6” and “visit 7”

- Collect AEs.
- Record concomitant medication.
- Perform physical examination (only in case of clinically relevant abnormality at the end of treatment visit) if visit at clinical site.

10.1.3.2 Second Follow-Up Visit (Visit 8 / Week 14 for Cohort 3/Day 98 ±7/ Week 16 for Cohorts 1 & 2 / Day 112 ±7) at clinical site (end of the main study period).

- Collect AEs.
- Record concomitant medication.
- Get body weight and height measurements.
- Take vital signs including HR and BP.
- Perform physical examination (only in case of clinically relevant abnormality at the Week 8/end of treatment visit).
- Get Tanner stages measurement by the same investigator/designee at each visit if possible.
- IVRS/IWRS contact to document the end of the main phase period and the start of the optional open-label extension period if patient agrees for participation in this extension.
- Urine pregnancy test (females who have experienced menarche only).
- Obtain fasting blood sample for:
 - Anti-alirocumab antibodies,
 - Serum alirocumab concentration (PK),
 - PCSK9 levels (free and total).

- Only in case of clinically relevant abnormal values for these parameters at the end of treatment visit will the following be obtained at this visit:
 - Hematology: red blood cell count including hematocrit, hemoglobin, WBC count with differential count and platelets,
 - Chemistry: glucose, sodium, potassium, chloride, bicarbonate, calcium, phosphorous, urea nitrogen, creatinine, uric acid, total protein, LDH, albumin, and γ GT,
 - Liver panel (ALT, AST, ALP and total bilirubin),
 - CPK.

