For Cohorts 1- 3, the initial dose of alirocumab that will be administered during the extension phase, will be the continuation of same doses/regimens administered during the main phase up to the time when the final optimal doses for the Phase 3 study are selected and prefilled syringes

available. Then these final optimal doses will be administered to all patients during the extension phase, based on their body weight at the time of dose change.

For Cohort 4, if patients enter the OLE phase, patients will continue on their doses from the main phase.

At the end of each study phase, patients are to be followed 10 weeks after last alirocumab injection on site (for main phase, only for Cohorts 1-3 as this follow up period doesn't apply for Cohort 4) or by phone (for extension phase, for all cohorts). Patients with any adverse event (AE) should be followed until resolution, stabilization, or death, as specified in the protocol.

Approximately 40 patients (10 patients per cohort) were to be enrolled from approximately 28 sites.

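### For the dose-finding period, the insufficient-follow-up rule in SAP 2.2 flags Cohort 4 patients who are dosed at Week 8 and then follow the planned schedule

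*SAP*

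**What the plan says.** SAP 2.2 sets up a disposition item as follows: "Patient with insufficient post-treatment follow-up will be described for each analysis study treatment period". The dose-finding (OLDFI) period is one of those periods, and no cohort is exempted. Two cases are listed:

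- The patient was not assessed at the final follow-up contact or at any on-site post-treatment visit.
- The patient has no telephone follow-up (OLE period) or "on-site post-treatment visit more than 9 weeks after the last IMP injection of the corresponding period". As worded, a telephone call counts for the OLE only.

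Elsewhere the documents treat Cohort 4 differently. SAP 1.1 says that the 10-week on-site follow-up in the main phase is "only for Cohorts 1-3 as this follow up period doesn't apply for Cohort 4". Protocol 10.1.3 says: "The follow-up period is mandatory for cohorts 1-3 but not for Cohort 4". SAP Table 3 likewise confines the follow-up window to Cohorts 1 to 3.

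For Cohorts 1-3, Protocol 6.1 puts the final follow-up visit 10 weeks after the last injection, "since the last injection for Cohorts 1 & 2 is Week 6 and for Cohort 3 it is Week 4".

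**The concern.** The rule asks for something that the Cohort 4 schedule does not contain. SAP version 2 was written to add Cohort 4, and the study-design text, the analysis windows and the imputation of the last-injection date were all adapted to it. The follow-up definition in SAP 2.2 was not.

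At stake is the meaning of one line of the disposition table. At the final OLDFI analysis it would label patients who did what the protocol asks as insufficiently followed, in the Q4W cohort with the higher doses, beside Cohorts 1-3, where the planned visit normally satisfies the rule. A reader could not tell from that line which Cohort 4 patients departed from the plan.

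A smaller question concerns Cohorts 1-3: whether the 9-week cut agrees with the windows that the protocol allows around a 10-week visit.

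**Working it through.** **Inputs**

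- Threshold: more than 9 weeks, that is more than 63 days (SAP 2.2).
- Last OLDFI injection: Week 6 = Day 42 (Cohorts 1-2) and Week 4 = Day 28 (Cohort 3), from Protocol 6.1; Week 8 = Day 56 (Cohort 4), from Protocol 1.1.2.
- Final follow-up visit, Cohorts 1-3: "Week 14 for Cohort 3/Day 98 ±7/ Week 16 for Cohorts 1 & 2 / Day 112 ±7" (Protocol 10.1.3).
- Last OLDFI visit, Cohort 4: Week 12 = Day 84 (Protocol 10.1.2), ±7 days in the flow chart (Protocol 1.3.2).
- Dosing window: "it is acceptable to have a window period of ± 3 days" (Protocol 8.1.2).

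**Formula**

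Interval = (visit day + v) − (injection day + i), with v from −7 to +7 and i from −3 to +3 in whole days. That gives 15 × 7 = 105 combinations. A combination is flagged if the interval is 63 days or less.

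**The plan's own figure**

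112 − 42 = 70 and 98 − 28 = 70 days, so the stated 10 weeks for Cohorts 1-3 is reproduced.

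**Results**

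| Cohort | Nominal interval | In-window range | Combinations flagged |
|---|---|---|---|
| 1-2 | 70 days | 60 to 80 | 10 of 105 |
| 3 | 70 days | 60 to 80 | 10 of 105 |
| 4 (dosed at Week 8) | 84 − 56 = 28 days | 18 to 38 | 105 of 105 |

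**Cohort 4.** The longest in-window interval, 38 days, falls 25 days short of 63. Nothing else in the SAP rescues a patient who continues:

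- For OLE entrants, SAP 2.1.4 ends the OLDFI post-treatment period on the day before the first OLE injection, which is given at Week 12. Later OLE visits therefore do not count.
- SAP 3 restricts the follow-up analysis to patients who have completed follow-up, but that restriction is written for the combined OLDFI/OLE analyses at the first analysis, which covers Cohorts 1 to 3.

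An early discontinuer is different. With the last injection at Week 0, the on-site Week 10 visit is 70 days later and passes. With the last injection at Week 4, the Week 12 visit is only 84 − 28 = 56 days later. Protocol 10.3.4 nevertheless requires at least 10 weeks of follow-up and allows an end-of-study visit at that point.

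**Cohorts 1-3.** A flag needs v − i ≤ −7:

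- v = −7 with i = 0, 1, 2 or 3 (4 combinations);
- v = −6 with i = 1, 2 or 3 (3);
- v = −5 with i = 2 or 3 (2);
- v = −4 with i = 3 (1).

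The total is 10, or 9.5% of combinations. This counts calendar combinations and does not predict a patient rate. With the injection exactly on time, only a visit on Day 105 (Cohorts 1-2) or Day 91 (Cohort 3) is caught, at exactly 63 days.

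**After a change of cut.** Requiring 63 days or more would still flag 6 of 105. Requiring 60 days or more flags 0 of 105.

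**The case against.** The best defence is that the flag is often correct. A Cohort 4 patient who stops at Week 12 has about 4 weeks of on-site follow-up, against a treatment-emergent period of 70 days after the last injection (SAP 2.1.4). Calling that insufficient is accurate, and the cause is the design. This stands, and it limits the complaint to patients who move on as planned.

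Three stronger readings are tempting, and the documents do not support them.

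- A reader might infer that every Cohort 4 patient fails. Early discontinuers can pass. A patient outside the OLE with an antibody titer of 240 or more returns for later samples (Protocol 8.3.3). In the OLE period the telephone contact satisfies the rule.
- A reader might infer that the table conceals patients who were lost. SAP 2.2 separately reports non-completion, discontinuation by reason, OLE participation, and status at last contact for those not entering the OLE. SAP 2.4 shows OLDFI results by cohort and dose group.
- A reader might take the Cohort 1-3 mismatch as a material error rate. Nine weeks is the planned ten less the 7-day visit window, so the cut is reasonable. What remains is the strict inequality and the 3-day dosing window.

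It can also be argued that both cases must hold before a patient is flagged. A Cohort 1-3 patient seen at the final visit would then escape. Cohort 4 would escape too if the Week 10 and Week 12 visits count as post-treatment. The wording lists them as cases, which reads more naturally as alternatives, but the SAP should say so.

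**Conclusion.** The point holds for the OLDFI period. A Cohort 4 patient dosed at Week 8 and seen on schedule cannot satisfy the second criterion: 28 days nominal and 38 at most, against more than 63. Those who continue into the OLE or Phase 3 as planned would be misdescribed. With about 10 patients planned in the cohort, that could be most of it; the documents do not give the split between continuing and stopping.

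The Cohort 1-3 effect is an edge case of 60 to 63 days and needs a final visit 4 to 7 days early.

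The conclusion assumes that the two criteria are alternatives and that an OLE visit is not an OLDFI post-treatment visit. The consequence is one descriptive disposition item. No efficacy estimate, analysis population or adverse-event window depends on it.

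**What to change.** Amend SAP 2.2 as follows.

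1. State that the two cases are alternatives.
2. Mark the OLDFI criterion not applicable to Cohort 4 patients who enter the OLE or go directly to Phase 3. OLE entrants are already assessed after their last OLE injection, so nothing is lost for them.
3. Report Cohort 4 patients who stop on a separate line, and credit the telephone contact at least 10 weeks after the last injection that Protocol 6.2.1 plans for all cohorts. A note to the Cohort 4 extension diagram (Protocol 1.2.2) excepts patients who refuse Phase 3, so the two places should be reconciled first. For the last patients this contact falls after the cut-off for the final OLDFI analysis (last Cohort 4 OLDFI visit), so show it as not yet due.
4. For Cohorts 1-3, count a final follow-up visit made within its protocol window as sufficient. With both windows respected this equals 60 days or more (70 − 7 − 3).

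The cost is a few lines of SAP text and a small programming change. No new data are needed.

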2.2.1 Enrollment and drug dispensing irregularities

Enrollment and drug-dispensing irregularities occur whenever:

1. An enrollment is not in accordance with the protocol-defined enrollment method, such as,
 - a patient is enrolled twice.

OR

2. A patient is dispensed an IMP kit not allocated by the protocol-defined allocation, such as
 - a patient at any time in the study is dispensed a different treatment kit than as allocated (which may or may not contain the correct-as-allocated IMP).

Enrollment and drug-dispensing irregularities will be monitored throughout the study and reviewed on an ongoing basis.

All enrollment and drug-dispensing irregularities will be documented in the clinical study report among included patients.

Enrollment and drug-dispensing irregularities to be prospectively identified include but are not limited to:

Enrollment and drug allocation irregularities
Kit dispensation without IRT transaction
Erroneous kit dispensation
Kit not available
Enrolled by error
Patient enrolled twice

2.3 ANALYSIS POPULATIONS

Included population: includes all included patients as defined in [Section 2.2](#).

For any patient included more than once, only the data associated with the first inclusion will be used in any analysis population. The safety experience associated with any later inclusion will be assessed separately.

2.3.1 Efficacy populations

The primary efficacy analysis population for OLDFI period and for the OLDFI/OLE combined period will be the mITT population.

2.3.1.1 *Modified intent-to-treat population*

The modified ITT (mITT) population includes all included patients who received at least one dose or partial dose of IMP injection and had an evaluable primary endpoint during the OLDFI efficacy treatment period. The primary endpoint will be considered as evaluable when both following conditions are met:

- Availability of baseline calculated LDL-C value.
- Availability of at least one calculated LDL-C value during the OLDFI efficacy treatment period and within one of the analysis windows up to Week 8 analysis window.

The OLDFI efficacy treatment period is defined as the period from the first IMP injection to last OLDFI IMP injection + 21 days (for Cohorts 1 & 2) or +35 days (for Cohorts 3 & 4). For patients entering in the OLE, the OLDFI efficacy treatment period will be truncated at the day before the first OLE IMP injection in the extension period.

Patients in the mITT population will be analyzed according to the alirocumab dose group allocated by IVRS.

2.3.2 Safety population

The Safety population considered for safety analyses in the OLDFI period and in OLDFI/OLE combined period will be the included population who actually received at least one dose or part of a dose of the IMP injection. Patients will be analyzed according to the dose of alirocumab actually received (ie, as-treated dose group, alirocumab 30 mg Q2W, alirocumab 40 mg Q2W, alirocumab 50 mg Q2W, alirocumab 75 mg Q2W, alirocumab 75 mg Q4W, alirocumab 150 mg Q4W [BW <50 kg], alirocumab 150 mg Q4W [BW ≥50 kg] or alirocumab 300 mg Q4W).

In addition:

- Included patients for whom it is unclear whether they took the study medication will be included in the safety population as assigned by IVRS.

- For patients receiving the 2 alirocumab doses planned for the cohort during the treatment period (cases reported as protocol deviation), the alirocumab dose used for as-treated analysis will be the one to which the patient was treated with the highest number of injections; in case of the same number of injections of each dose received the as-treated dose will be the as-randomized dose.

